#### 5.0 Study population

The target study population are males and females aged 18 or older who have moderate to severe FI, defined as a minimum average frequency of staining, solid or liquid FI events at least 2/week using the baseline bowel diary. Patients will be recruited by a variety of methods: Direct referrals from clinicians, patients with a diagnosis of FI in their medical record (ICD 10 diagnosis code R15), registries of research participants with FI who have participated in previous studies of FI treatment, and advertisements in newsletters, newspapers, on websites, or flyers posted in medical or surgical clinics. Information on how the patient learned about the study will be collected at their screening visit.

#### 5.1 Inclusion/ Exclusion criteria

Inclusion Criteria	Exclusion Criteria
Physician diagnosis of FI (R15) for the past 6 months or longer. We will recruit some subjects by advertisement who may not have consulted a physician, and this diagnosis may be made by the study physician. Able to ambulate independently on level surfaces. Patient may use	Dementia will be assessed using the Six-Item Screener to Identify Cognitive Impairment. The subject is asked to remember 3 words (apple, table, penny), which may be repeated up to 3 times. This is followed by 3 questions on the year, month, and day of the week. Finally, the subject is asked to recall the three words. Three or more errors has a sensitivity of 88.7% and specificity of 88.0% compared to clinical diagnosis and is not different from the Mini Mental State Exam. [Callahan, CM et al. Six-Item Screener to Identify Cognitive Impairment among Potential Subjects for Clinical Research. Medical Care 2002;40:771-81.] Obstetrical injuries including third and fourth degree tears in the anal sphincter within 6 months.
assistive devices other than parallel bars.	
Average ≥2 solid, liquid, or staining FI episodes per week by self-report and during the two-week baseline	Pregnant or planning pregnancy in next 2 years
Meets criteria for dextranomer treatment except an internal anal sphincter defect of 180 degrees or less is acceptable.	Internal anal sphincter separation >180 degrees on ultrasound or magnetic resonance imaging
Required for randomization: Less than 75% reduction in the number of FI episodes after 4 weeks of EMM.	Spinal cord injury or spina bifida
Age >=18 years	Congenital malformation of anorectum
	Complete rectal prolapse or grade III/IV hemorrhoids
	History of ileoanal pouch; history of anal sphincteroplasty, rectopexy, or rectocele repair within the past 6 months; or history of pelvic surgery with synthetic graft and suspected graft erosion into the anus, rectum, or skin or if the graft ends less than approximately 1" above the upper limit of the anal canal.
	Established diagnosis of inflammatory bowel disease
	Intestinal stoma present
	History of pelvic radiation within previous 12 months or presence of active radiation proctitis.
	Patients who cannot expel the rectal balloon during the balloon expulsion test and who have constipation most of the time.
	Anatomic limitations to placement of dextranomer injections.
	Presence of existing implant in the anorectal region
	Allergy to hyaluronic acid-based products
	Active anorectal conditions in the last 6 months including abscess, fissures, sepsis, significant bleeding, proctitis, colovaginal and rectovaginal fistulas, anorectal tumors, or other infections.
	If the patient's physician believes it is unsafe for the patient to temporarily stop anticoagulants for any test procedures and treatments associated with the study.
	Patients who have 4 or more days with 4 or more bowel movements classed as a 6 or 7 on the Bristol Stool Scale per day in either (any) week during the Baseline will be excluded.
	Patients with Parkinson's disease, multiple sclerosis, severe diabetic neuropathy documented by EMG, and neurodegenerative disorder.
	Patients currently receiving immunotherapy or chemotherapy
	Significant anal pain in the last 6 months.
	If the patient is unwilling to stop using over-the-counter medications, herbal supplements, or prescribed medications for the purpose of modifying stool consistency, that are not included in the approved medications list (loperamide, laxatives, fiber supplements, and Questran are approved medications), for the duration of the research study.

Medical history will be documented to test for predictors of response.

## 5.2 Sample Size Estimates

## 5.2.1. Primary Efficacy Outcome

Sample-size calculations are based on the number of patients required to detect a difference of 20% in the proportion of responders because we consider this to be the Minimum Clinically Important Difference (MCID) between groups following treatment. Table 3 shows the sample data used in these calculations, which comes from published pivotal trials for dextranomer and biofeedback. Conservatively assuming an average response rate of 50% across the groups, an alpha of .05 and power of 80% we would need at least 97 patients per group to test for differences of this magnitude between 2 treatment groups. Since the planned analysis will use an intention to treat (ITT) approach in which all participants will have a defined efficacy outcome regardless of study completion, this sample size was not inflated to account for potential drop out.

The data in Table 3 suggest that we have an excellent chance of detecting a difference of 20% and of showing that BIO is superior to INJ in the proposed trial. We should also be able to show significant differences between BIO and the other two treatments for adverse events, estimated cost of care, percent continent, and impact of FI on quality of life (Table 4).

Efficacy Outcome Measure	BIO Heymen 	INJ Graf 	Sample size required per group
Baseline: FI days per week	3.4 (SD=2.1)	4.8	
> 50% decrease (%)	93%	53%	28
> 75% decrease (%)	78%	32%	28
Continent (%)	44%	5.9%	29

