Graf reported there were 128 adverse events and two serious adverse events (AEs) in the 136 patients who received INJ. However, many of these were minor AEs related to changes in stool consistency. The incidence of more significant AEs, such as pain, fever, and/or abscess, was 9.6%. Other investigators have reported comparable rates of AEs in uncontrolled case series. Dextranomer treatment is not consistently reimbursed by third party payers but is estimated to cost approximately \$7,408 if two injections are given

2.2.3. Sacral Nerve Stimulation: SNS is performed in two steps: (1) During test stimulation, a temporary electrode is inserted with its tip near the sacral nerve and connected to an external stimulator for 1-2 weeks. However, screening procedures are evolving, with many surgeons now preferring to use barbed leads intended for permanent implant during the screening stage, reasoning that 70% to 90% of patients will improve enough to warrant a permanent implant, and for these patients, the permanent lead is already in place. In this study, we plan to use the tined lead to avoid the need for a second test if the PNE fails. (2) If FI frequency decreases by at least 50% during PNE, a battery-operated electrical stimulator is permanently implanted beneath the skin. An estimated 10% - 30% of patients fail to meet criteria for permanent implant. Publications on the effectiveness of SNS often report only the outcomes for patients receiving permanent implants, but this makes these outcomes not comparable to reports on BIO and INJ where the analysis sample includes all patients randomized to treatment (intent-to-treat analysis). Consequently, in the literature review below, we adjust for the number of patients failing test stimulation and report the intention-to-treat (ITT) outcomes for SNS.

Although SNS is regarded as standard of care for patients with severe FI who have failed enhanced medical treatment and is approved by the FDA for this indication, few RCTs have been published. Wexner reported a large, uncontrolled multisite study, and this carefully done study was used for our sample size calculations. This study included 133 patients with at least two episodes of solid or liquid FI per week at baseline. After correction for patients who failed the test stimulation, the proportion achieving a 50% reduction by ITT analysis was 71.4% at six months and 66.2% at 12 months.

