## Table 7. Randomized treatment non-responders and estimated number followed at 6, 12 and 24 months

Randomized treatment	Non-responders at 3 months	Followed to 6 months	Followed to 12 months	Followed to 24 months
BIO	17	17	15	13
INJ	63	60	53	45

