#### 5.4 Estimated patient flow for this study

Figure 3 shows the estimated flow of patients through this study and identifies our assumptions regarding attrition. We estimate we will need to screen 855 patients because 2/3 will be ineligible or unwilling to be randomized. This leaves 285 to be recruited into the EMM protocol. Based on the Heymen study, we assume

15% attrition during this treatment phase and also assume that 20% (n=57) will be responders to EMM and therefore not eligible for randomization. This will leave 194 to be randomized (97 per group).

Figure 3 shows that we expect 78 from the BIO group to complete the 3-month assessment after allowing for attrition of 20% and we expect 92 from the INJ group to complete the 3-month assessment. (We assume attrition will be no greater than 5% for the INJ group because this is a low-burden treatment and also because patients will want to be screened for AEs related to INJ.) However, the statistical analysis will be by intent to treat (ITT) and will include all 194 randomized to treatment; patients who are lost to follow up prior to 3 months will be considered treatment failures. The number of patients we expect to be responders to each of the treatments at the 3-month assessment is based on the pivotal trials shown in Table 1. We separated them in this way in Figure 3 to be able to estimate the numbers of non-responders who are likely to choose an additional treatment option after 3 months. The expected number of non-responders eligible for an additional therapy at 3 months is 63 for the INJ arm^16 and 17 for the biofeedback arm^15. Assuming equal probability of choosing either of the 2 available options as an added or alternative treatment, we could expect 40 patients to choose the SNS treatment, 32 to choose BIO, and 9 to choose INJ. For the primary analyses of follow up at 6, 12 and 24 months, these non-responders will be retained in the ITT analysis as non-responders to their primary assignment at randomization. However, when we perform exploratory analyses of treatment combinations, these subjects will be treated as distinct groups and compared to patients who received monotherapy for the duration of the study. These comparisons (Aim D) are exploratory because there is insufficient power to test for significance. The left column of boxes in Figure 3 shows how we intend to follow up the responders to EMM.

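### Does leaving out a dropout allowance in Section 5.2.1 undercut the stated 80% power, given unequal attrition counted as failure?

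*Combined protocol and SAP*

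**What the plan says.** Section 5.2.1 takes 20 percentage points as the minimum clinically important difference in the proportion of responders and assumes an average rate of 50%. It concludes that with "an alpha of .05 and power of 80% we would need at least 97 patients per group" the trial can test for that difference. It adds no allowance for dropout, on the ground that under ITT "all participants will have a defined efficacy outcome regardless of study completion, this sample size was not inflated to account for potential drop out".

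Section 5.4 gives the attrition assumptions. For BIO, "we expect 78 from the BIO group to complete the 3-month assessment after allowing for attrition of 20" per cent. For INJ, "We assume attrition will be no greater than 5% for the INJ group because this is a low-burden treatment". It states that the analysis covers all 194 randomized patients and that "patients who are lost to follow up prior to 3 months will be considered treatment failures". Section 8.1 applies the same rule to anyone without a valid 3-month diary and commits to sensitivity analyses of that rule.

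Two places bear on the scale of the published response rates. Section 2.2.3 contrasts reports on sacral nerve stimulation with "reports on BIO and INJ where the analysis sample includes all patients randomized to treatment (intent-to-treat analysis"). Section 5.4, in projecting who will be offered a second treatment, says: "The expected number of non-responders eligible for an additional therapy at 3 months is 63 for the INJ arm", with 17 for the biofeedback arm. These counts open Table 7 ("Randomized treatment non-responders and estimated number followed at 6, 12 and 24 months").

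**The concern.** Giving every participant an outcome fixes the denominator at 97, but it does not by itself fix the treatment difference. If dropouts are scored as failures and four times as many are expected on BIO as on INJ, any BIO advantage among patients actually assessed is diluted, and any INJ advantage is enlarged. Section 5.2.1 does not say in words whether its 20 points are measured before or after that step. If they were measured before, the stated 80% would be wrong in both directions: too high for a BIO lead and too low for an INJ lead. A non-significant result with BIO ahead could then be misread as good evidence against a 20-point benefit.

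The plan also seems to use two scales. Section 2.2.3 describes the BIO and INJ literature as analysing everyone randomized, while Section 5.4 applies the rates in Table 3 to assessed patients only.

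**Working it through.** **Inputs.** 97 per group, alpha 0.05, power 80%, 20-point difference and 50% average (hence 60% vs 40%) from Section 5.2.1. 1:1 allocation from Section 7.1. Attrition of 20% (BIO) and 5% (INJ) from Section 5.4. Rates of 78% (BIO) and 32% (INJ) from Table 3. A two-sided test is inferred from the no-difference null in Section 8.1; a one-sided test would need 77 per group, not 97.

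**1. The plan's own figure.** Pooled two-proportion formula, no continuity correction:

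n = [1.960·√(2·p̄·q̄) + 0.842·√(p₁q₁ + p₂q₂)]² / d²

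= [1.960·√0.50 + 0.842·√0.48]² / 0.20² = 96.9, so 97.

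Power at 97 for 60% vs 40% is 80.0%. The stated figure reproduces exactly.

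**2. If the 20 points were among assessed patients.** ITT rate = assessed rate × (1 − attrition). Power = Φ{[d·√n − 1.960·√(2·p̄·q̄)] / √(p₁q₁ + p₂q₂)}.

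| Assessed rates | ITT rates | ITT difference | Power, n = 97 |
|---|---|---|---|
| BIO 60%, INJ 40% | 0.60×0.80 = 48%; 0.40×0.95 = 38% | 10 points, BIO ahead | 28.9% |
| BIO 40%, INJ 60% | 0.40×0.80 = 32%; 0.60×0.95 = 57% | 25 points, INJ ahead | 94.5% |

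For the first row: [0.10×9.849 − 1.960×0.700] / 0.697 = −0.556, and Φ(−0.556) = 0.289. Simulation gave 29.2%. The result depends on the 50% average: for assessed averages from 30% to 70% with BIO 20 points ahead, power runs from 55% down to 17%. It also depends on INJ attrition, for which 5% is a ceiling: with none, the contrast is 48% vs 40% and power is 20%.

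**3. Which scale the sample size uses.** Section 5.2.1 bases N on the responder proportion and, in the same paragraph, says the analysis is ITT with an outcome for everyone. Section 5.4 puts all 194 in the analysis with losses as failures. Section 8.1 tests that same proportion under that same rule. A sample size for a primary test ordinarily refers to the quantity tested, and here that is the ITT proportion. Step 1 therefore applies, and inflation would be redundant.

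**4. The basis of the Table 3 rates.** In Section 5.4, 97×0.80 = 77.6 (78 assessed) and 97×0.95 = 92.2 (92 assessed). Non-responders: 78×0.22 = 17.2 (17 stated) and 92×0.68 = 62.6 (63 stated). So the projection does treat 78% and 32% as rates among assessed patients. The expected ITT rates are then (78 − 17)/97 = 62.9% and (92 − 63)/97 = 29.9%, a gap of 33 points rather than the 78 − 32 = 46 in Table 3. Power for 62.9% vs 29.9% is 99.7%.

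If Table 3 instead held ITT rates with dropouts as failures, BIO responders would be 0.78×97 = 75.7, leaving 78 − 75.7 = 2.3 assessed non-responders. INJ would have 92 − 0.32×97 = 61.0.

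**The case for a change.** The best case for a change is that the text never names the scale, that Section 5.4 uses the assessed scale for rates from the same published trials, and that the asymmetry is large. A 20-point ITT difference at 60% vs 40% corresponds to 0.60/0.80 − 0.40/0.95 = 33 points among assessed patients if BIO leads, but only 0.60/0.95 − 0.40/0.80 = 13 points if INJ leads. The sensitivity analyses in Section 8.1 examine the missing-data rule afterwards; they do not define the design difference. A clause would cost nothing.

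The arithmetic stands, and so does the observation that the scale is unwritten. The inference to a power shortfall does not. The two-scale evidence concerns the Table 3 rates, whereas the 20 points are a clinical judgement and the 50% a conservative average; neither is derived from 78% and 32%. The contrast of about 2 against 17 non-responders is conditional: it needs the cited trials to have scored dropouts as failures, which Section 2.2.3 does not say, and it needs this trial's 20% attrition. The counts in question feed the treatment-combination aim, which Section 5.4 calls exploratory for lack of power and for which Section 5.3 already plans group sizes anywhere from 5 to 50.

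**Conclusion.** The concern does not hold as a fault in the sample size. With the 20 points read as the ITT difference that Section 8.1 tests, 97 per group delivers the stated 80.0% and no dropout inflation is due. The 29% is power for a different alternative: a 20-point BIO lead among assessed patients, at a 50% average, with 20% and 5% attrition. With INJ ahead by the same margin it would be 94.5%. At the rates Section 5.4 expects, power is 99.7%.

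What remains is missing detail: one unstated scale, which Sections 5.4 and 8.1 let the reader supply, and one unstated basis for Table 3, which affects only planning counts for an exploratory aim. Writing either down would leave N, the primary model, the handling of missing diaries and the sensitivity analyses exactly as they are. The figures rest on an unadjusted two-sided two-proportion test, which the plan's 97 matches; the planned logit model also adjusts for site and sex.

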#### Table 3: Preliminary Data for Sample Size Calculations

#### Table 4: Preliminary Data on Other Outcome Measures

Outcome Measure	BIO Heymen 	INJ Graf 	Sample size required per group
 Adverse events (% subjects)	0%	9.6%	74
 Estimated cost (\$)	\$1,435	\$7,408	
 % Change in quality of life impact	11.9% (SD = 21.5)	27.3%	32
 St Mark's Score or FISI, Average % decrease	36% (SD = 45.8)	17.9%	102

There were 128 AEs in 136 patients, but some were relatively minor. We list only the estimated rate of pain, fever, and abscess (13 events in 136 patients). Sample size calculations are for tests of proportions with alpha = .05 and beta = .80. Costs are estimated from published Medicare reimbursement tables are not compared statistically.

Continuous outcomes for quality of life and FI severity calculations assume alpha = .05 and beta = .80.

It is anticipated that up to 15% of participants enrolled in the study will drop out (with no further follow up). before completing enhanced medical treatment. If the number who drop out exceeds 15%, additional subject will be recruited and enrolled into the study, but prior research suggests that 15% is a reasonable estimate. Another 15-20% are expected to achieve a 75% reduction in FI during EMM and will need to be replaced Thus,

we anticipate that approximately 285 participants will need to begin EMM treatment in order for 194 to complete the run-in phase and be randomized to BIO or INJ (97 per group). The participant flow diagram is shown in Figure 3.

#### 5.2.2. Primary Safety Outcome

For the primary safety outcome, we will use Fisher's exact tests to compare the percentage of participants in the two randomized treatment groups who experience an adverse event (AE) of pelvic pain of grade II or greater severity, treatment site infection, or a serious adverse event (SAE) requiring hospitalization between randomization and the 3-month assessment. For this analysis, participants who are missing safety data will be excluded from analysis, but we assume that 78 in the BIO group and 92 in the INJ group will be available for evaluation at 3 months and that those numbers represent the minimum number of participants who will be included in the primary safety analysis. Based on previous studies, we expect the percentages of participants with a qualifying AE or SAE to be approximately 9.8% (9/92) in the INJ group, and 0% (0/78) in the BIO group. The anticipated sample size will provide 83% power to detect a pairwise difference between percentages of 0 and 10% at an alpha of 0.05.

## 5.2.3. Primary Cost Outcome

Analysis of Cost from the Payer Perspective. To perform power calculations for the difference in 3 month treatment costs, we used cost estimates for treatment provided in Bernstein and described below. As standard deviations were not provided in the text, we assumed a standard deviation of 0.5 (UB-LB). Sample sizes are based on the number of participants in each treatment group who are expected to be evaluated at the primary endpoint.

- BIO treatment was estimated at \$265.45 (\$212.36-318.55) per month. Treatment cost in Table 5 is provided for 3 months.
- Physician and device costs (ranges) for INJ treatment was: \$281.03 (\$224.82-337.23) and \$4,900 (\$2,940-6,860). We assumed two injections per participant in the first 3 months, and summed them to produce the treatment cost in the table.

	Treatment Cost	Sample Size	Standard Deviation
BIO	\$796	103	160
INJ	\$10,363	123	4,032

#### Table 5. Assumptions underlying power analysis for medical costs of FIT treatments for 3 months

Performing analysis with an alpha of 0.05 results in a power of 1.0 given that the differences in expected treatment costs are so large.

Analysis of Cost from the Societal Perspective. To perform power calculations for the difference in 3-month societal costs, we added treatment cost estimates provided in Table 5 to 3 month medical and productivity costs associated with FI, adjusted by treatment. Medical and productivity FI costs were taken from Xu. Given lack of data on the extent to which each treatment may impact medical and productivity costs of FI, we incorporated the assumptions outlined below (Table 6). Annual direct and indirect medical costs are estimated to be \$2,562, and annual productivity costs are estimated at \$1,549. We multiplied these costs by 0.25 to estimate 3-month costs.

- BIO was assumed to reduce FI medical costs by 25%, and productivity costs by 0%.
- INJ was assumed to reduce FI medical costs by 50% and productivity costs by 25%.

	Societal Cost	Sample Size	Standard Deviation
BIO	\$1,664	103	2,138
INJ	\$10,973	123	5,448

# Table 6. Assumptions underlying power analysis for societal costs of FIT treatments for 3 months

Performing analysis with an alpha of 0.05 results in a power of 1.0 given the large, expected difference in societal costs between the treatments.

## 5.3. Secondary Aim to Evaluate Treatment Combinations

A secondary aim of the study is to evaluate treatment-order combinations after participants are allowed to cross over into other study arms. At the 3-month assessment, non-responders to randomized treatment can choose to initiate an additional treatment. This is a pragmatic approach reflecting the reality that patients in clinical care who are not happy with their initial FI treatment may choose to try another treatment. Table 7 shows the number of 3-month non-responders in each randomization group who are expected to be followed to 6, 12 and 24 months with the assumption of 15% attrition (loss to follow up or missing outcomes for other reasons) between the 3- and 12-month assessments and an additional 15% attrition between the 12- and 24-month assessments. Since non-responders can choose to try the other study treatment or SNS after 3 months, we estimate that between 5 and 50 participants will be in each of the possible treatment-order combinations at 6, 12 and 24 months. We will estimate 95% confidence intervals for the number of responders in each treatment-order combinations at 6, 12 and 24 months. We will estimate 95% confidence intervals for the number of responders in each treatment-order combinations at 6, 12 and 24 months. We will estimate 95% confidence intervals for the number of responders in each treatment-order combinations at 6, 12 and 24 months. We will estimate 95% confidence intervals for the number of responders in each treatment-order combination at each time point. Table 8 shows 95% confidence intervals for a range of group sizes and responder percentages; confidence intervals are estimated using a Wilson Score interval recommended for small sample sizes.

